## Change #10

### 12.2.1 Analysis of the primary variable

#### **Additional study information:**

The retention analysis will be repeated on the modified FAS as a sensitivity analysis to represent the retention of patients who take BRV per the SmPC. In addition, a Kaplan-Meier analysis of time to discontinuation of BRV or study termination will be provided on the FAS and may be repeated on the modified FAS.

## Change #11

### 12.2.2 Analysis of secondary variables

The following variables will be summarized using descriptive statistics:

- Absolute and percent reduction in POS frequency (seizures per 28 days) from Visit 1 (Baseline) to Visit 2 (Month 3), Visit 3 (Month 6), and Visit 4 (Month 12 or end of Observation Period)

The following variables will be summarized using number and percentage:

- Responders, defined as a patient experiencing a  $\geq 50\%$  reduction in POS frequency (seizures per 28 days), from Visit 1 (Baseline) to Visit 2 (Month 3), Visit 3 (Month 6), and Visit 4 (Month 12 or end of Observation Period)
- Seizure-free status at Visit 2 (Month 3), Visit 3 (Month 6), and Visit 4 (Month 12 or end of Observation Period)

The time to first seizure from the date of first dose of BRV will be analyzed using Kaplan-Meier methods, from which the median time to first seizure will be calculated, along with 25% and 75% quartiles.

#### **Has been changed to:**

The following variables will be summarized using descriptive statistics:

- Absolute and percent reduction in POS frequency (seizures per 28 days) from Visit 1 (Baseline) to Visit 2 (Month 3), Visit 3 (Month 6), Visit 4 (Month 12), and Visit 4 (Month 12 and end of Observation Period)

The following variables will be summarized using number and percentage:

- Responders, defined as a patient experiencing a  $\geq 50\%$  reduction in POS frequency (seizures per 28 days), from Visit 1 (Baseline) to Visit 2 (Month 3), Visit 3 (Month 6), Visit 4 (Month 12), and Visit 4 (Month 12 and end of Observation Period)

- Seizure-free status at Visit 2 (Month 3), Visit 3 (Month 6), Visit 4 (Month 12), and Visit 4 (Month 12 and end of Observation Period)

The time to first seizure from the date of first dose of BRV will be analyzed using Kaplan-Meier methods, from which the median time to first seizure will be calculated, along with 25% and 75% quartiles.

These analyses will be performed on the FAS and may be repeated on the modified FAS.

## Change #12

### 12.2.3 Analysis of other variables

The following variables will be summarized using descriptive statistics:

- QOLIE-31-P: 7 multi-item subscales, health status item, and total score for the showing observed results and the change from Visit 1 (Baseline) to Visit 2 (Month 3), Visit 3 (Month 6), and Visit 4 (Month 12 or end of Observation Period)
- Total EpiTrack score and the individual scores of the 6 subtests showing observed results and the change from Visit 1 (Baseline) to Visit 3 (Month 6) and Visit 4 (Month 12 or end of Observation Period)
- Change in drug load of AEDs from Visit 1 (Baseline) to Visit 4 (Month 12 or end of Observation Period)

The following variables will be summarized using number and percentage:

- Patients with a clinically meaningful change in QOLIE-31-P from Baseline (improvement, no change, or worsening, based on the minimally important change; Borghs et al, 2012) to Visit 2 (Month 3), Visit 3 (Month 6), and Visit 4 (Month 12 or end of Observation Period)
- Patients in each of the cognitive performance categories using the EpiTrack tool (excellent, average, mildly impaired, or significantly impaired) at Visit 1 (Baseline), Visit 3 (Month 6), and Visit 4 (Month 12 or end of Observation Period)
- Patients in change categories of cognitive function (improved, unchanged, or worsened) between the visits (from Visit 1 [Baseline] to Visit 3 [Month 6] and to Visit 4 [Month 12 or end of Observation Period] and from Visit 3 [Month 6] to Visit 4 [Month 12 or end of Observation Period]) based on the assessments using the EpiTrack tool
- Patients with each CGIC and PGIC rating at Visit 2 (Month 3), Visit 3 (Month 6), and Visit 4 (Month 12 or end of the Observation Period)
- Patients who improved, had no change, and worsened in CGIC and PGIC

### Has been changed to:

The following variables will be summarized using descriptive statistics:

- QOLIE-31-P: 7 multi-item subscales, health status item, and total score for the showing observed results and the change from Visit 1 (Baseline) to Visit 2 (Month 3), Visit 3 (Month 6), Visit 4 (Month 12), and Visit 4 (Month 12 and end of Observation Period)

- Total EpiTrack score and the individual scores of the 6 subtests showing observed results and the change from Visit 1 (Baseline) to Visit 3 (Month 6) and Visit 4 (Month 12)
- Change in drug load of AEDs from Visit 1 (Baseline) to Visit 4 (Month 12) and Visit 4 (Month 12 and end of Observation Period)

The following variables will be summarized using number and percentage:

- Patients with a clinically meaningful change in QOLIE-31-P from Baseline (improvement, no change, or worsening, based on the minimally important change; Borghs et al, 2012) to Visit 2 (Month 3), Visit 3 (Month 6), Visit 4 (Month 12), and Visit 4 (Month 12 and end of Observation Period)
- Patients in each of the cognitive performance categories using the EpiTrack tool (excellent, average, mildly impaired, or significantly impaired) at Visit 1 (Baseline), Visit 3 (Month 6), and Visit 4 (Month 12)
- Patients in change categories of cognitive function (improved, unchanged, or worsened) between the visits (from Visit 1 [Baseline] to Visit 3 [Month 6] and to Visit 4 [Month 12] and from Visit 3 [Month 6] to Visit 4 [Month 12]) based on the assessments using the EpiTrack tool
- Patients with each CGIC and PGIC rating at Visit 2 (Month 3), Visit 3 (Month 6), Visit 4 (Month 12), and Visit 4 (Month 12 and end of the Observation Period)
- Patients who improved, had no change, and worsened in CGIC and PGIC

These analyses will be performed on the FAS and may be repeated on the modified FAS.

## Change #13

### 12.2.4 Analysis of tolerability and safety variables

For each of the following event types, frequency tables with the number of events, the number of patients who experience the event, and the percentage of patients who experience the event will be presented by MedDRA system organ class and preferred term:

- ADRs
- ADRs with an incidence  $\geq 5\%$
- Serious ADRs
- ADRs leading to permanent discontinuation of BRV

### Has been changed to:

### 12.2.4 Analysis of other tolerability and safety variables

For each of the following event types, frequency tables with the number of events, the number of patients who experience the event, and the percentage of patients who experience the event will be presented by MedDRA system organ class and preferred term:

- Treatment-emergent AEs and ADRs
- Treatment-emergent AEs and ADRs with an incidence  $\geq 5\%$

- Serious treatment-emergent AEs and ADRs
- ADRs leading to permanent discontinuation of BRV

These analyses will be performed on the SS and may be repeated on the modified FAS.

## Change #14

### 12.3 Planned interim analysis and data monitoring

Two nonformal interim analyses (snapshot analyses) are planned in this NIS. In order to assess early treatment effectiveness, as follows:

- A first snapshot analysis is to be performed with a data cut-off date approximately at the end of 2016 or when 80 patients have completed Visit 2 (Month 3), whichever occurs first. All patients with available data in the database will be included in the analyses.
- A second snapshot analysis is to be performed with a data cut-off date approximately at the end of 2017, depending on recruitment status.

### Has been changed to:

Three nonformal interim analyses (snapshot analyses) are planned in this NIS. In order to assess early treatment effectiveness, as follows:

- A first snapshot analysis is to be performed with a data cut-off date approximately at the end of 2016 or when 80 patients have completed Visit 2 (Month 3), whichever occurs first. All patients with available data in the database will be included in the analyses.
- A second snapshot analysis is to be performed with a data cut-off date approximately at the end of 2017, depending on enrollment status.
- A third snapshot analysis may be performed, if needed.

## Change #15

### 12.4 Determination of sample size

A sample size of 430 patients was chosen for this study in order to obtain 385 patients in the FAS, which allows for approximately 10% of subjects to not be included.

When the sample size is 385, a 2-sided 95.0% CI for a single proportion using the large sample normal approximation will extend 0.05 from the observed proportion for an expected proportion of 0.50. As an example, given an observed retention rate of 50%, a sample size of 385 patients would give a 2-sided 95% CI of 45% to 55% based on the large sample normal approximation to the binomial distribution.

It is, therefore, planned to have 430 patients, and withdrawals will not be replaced.

### Has been changed to:

Initially, a sample size of 430 patients was chosen for this study in order to obtain 385 patients in the FAS, which allows for approximately 10% of patients to not be included.

When the sample size is 385, a 2-sided 95.0% CI for a single proportion using the large sample normal approximation will extend 0.05 from the observed proportion for an expected proportion of 0.50. As an example, given an observed retention rate of 50%, a sample size of 385 patients

---

would give a 2-sided 95% CI of 45% to 55% based on the large sample normal approximation to the binomial distribution.

However, since the first 100 patients were all enrolled at sites in Germany in early 2016 and the enrollment in that country was closed, it was believed that ongoing enrollment in other countries would be following different best practices in BRV usage, which could lead to wide variation in this NIS. For this reason, 100 additional patients are planned to be enrolled to obtain 385 patients at non-German sites.

It is, therefore, planned to have 530 patients in this NIS. Withdrawals will not be replaced.

REDACTED COPY  
This document cannot be used to support any marketing authorization application and any extensions or variations thereof

---

## LIST OF ABBREVIATIONS

ADR	adverse drug reaction
AED	antiepileptic drugs
BID	“bis in die”/twice daily
BRV	brivaracetam
CGIC	Clinical Global Impression of Change
CI	confidence interval
CRO	contract research organization
CSR	Clinical Study Report
CRF	Case Report form
DDD	Defined Daily Dose
DEM	data evaluation meeting
FAS	Full Analysis Set
FDA	Food and Drug Administration
ICH	International Conference on Harmonization
LEV	levetiracetam
MedDRA	Medical Dictionary for Regulatory Activities
NA	Not applicable
NIS	noninterventional study
OSR	Other safety relevant
PGIC	Patient's Global Impression of Change
POS	partial-onset seizure
PT	Preferred Term
QOLIE-31-P	Patient Weighted Quality of Life in Epilepsy Inventory-Form 31

SAP	Statistical Analysis Plan
SAS	Statistical Analysis System
SD	standard deviation
SOC	System Organ Class
SOP	standard operating procedures
SS	Safety Set
SmPC	summary of product characteristics
TFLs	tables, figures and listings
VNS	vagus nerve stimulation
WHODD	World Health Organization Drug Dictionary

REDACTED COPY  
This document cannot be used to support any marketing authorization application and any extensions or variations thereof

## 1 INTRODUCTION

The purpose of this statistical analysis plan (SAP) is to provide all information that is necessary to perform the required statistical analysis of data collected in EP0077. It also defines the summary tables, figures and listings (TFLs) to be included in the final Clinical Study Report (CSR) according to the protocol.

This SAP is based upon, and assumes familiarity with, the Final Protocol Amendment 1, dated 25-Oct-2018.

If a future protocol amendment necessitates a substantial change to the statistical analysis of the study data, this SAP will be amended accordingly.

The content of this SAP is compatible with the International Conference on Harmonization (ICH)/ Food and Drug Administration (FDA) E9 Guidance documents (ICH E9, 1998).

UCB is the Sponsor and PRA Health Sciences is the contract research organization (CRO) for this study.

## 2 PROTOCOL SUMMARY

### 2.1 Study objective(s)

#### 2.1.1 Primary objective(s)

The primary study objective is to evaluate the effectiveness of brivaracetam (BRV) in patients with epilepsy with partial-onset seizures (POS) with or without secondary generalization in daily clinical practice.

#### 2.1.2 Secondary objective(s)

The secondary objective is to evaluate seizure control with BRV treatment.

### 2.2 Study variables

#### 2.2.1 Primary variable

The primary variable is the BRV retention at 12 months (end of Observation Period).

Note: This variable is used as a measure of effectiveness.

#### 2.2.2 Secondary variables

The following secondary variables will be measured:

- BRV retention at 3 months
- BRV retention at 6 months
- Absolute reduction in POS frequency (seizures per 28 days) from Baseline to 3 months
- Absolute reduction in POS frequency (seizures per 28 days) from Baseline to 6 months
- Absolute reduction in POS frequency (seizures per 28 days) from Baseline to 12 months
- Absolute reduction in POS frequency (seizures per 28 days) from Baseline to end of Observation Period
- Percent reduction in POS frequency (seizures per 28 days) from Baseline to 3 months

- Percent reduction in POS frequency (seizures per 28 days) from Baseline to 6 months
- Percent reduction in POS frequency (seizures per 28 days) from Baseline to 12 months
- Percent reduction in POS frequency (seizures per 28 days) from Baseline to end of Observation Period
- Response based on percent reduction in POS (seizures per 28 days) at 3 months (response is a reduction of  $\geq 50\%$ )
- Response based on percent reduction in POS (seizures per 28 days) at 6 months (response is a reduction of  $\geq 50\%$ )
- Response based on percent reduction in POS (seizures per 28 days) at 12 months (response is a reduction of  $\geq 50\%$ )
- Response based on percent reduction in POS (seizures per 28 days) at end of Observation Period (response is a reduction of  $\geq 50\%$ )
- Seizure freedom at 3 months
- Seizure freedom at 6 months
- Seizure freedom at 12 months
- Seizure freedom at end of Observation Period
- Time to first seizure after first dose of BRV

### 2.2.3 Other variables

The following other variables will be measured:

- Patient Weighted Quality of Life in Epilepsy Inventory-Form 31 (QOLIE-31-P) total and subscale scores at 3, 6, and 12 months and change in QOLIE-31-P scores from Baseline to 3, 6, and 12 months and end of Observation Period
- Presence of clinically meaningful change from Baseline to 3, 6 and 12 months and end of Observation Period in QOLIE-31-P
- EpiTrack® performance at 6 and 12 months
- EpiTrack change category from Baseline to 6 and 12 months and from 6 months to 12 months
- EpiTrack total score at 6 and 12 months and change from Baseline to 6 and 12 months
- EpiTrack total and individual subtest scores at 12 months and change in EpiTrack scores from Baseline to 12 months
- Clinical Global Impression of Change (CGIC) rating at 3, 6, and 12 months and end of Observation Period
- Patient's Global Impression of Change (PGIC) rating at 3, 6, and 12 months and end of Observation Period

- Change in drug load (ie, number of products, daily dose per given product, ratio of dose and Defined Daily Dose [DDD, [http://www.whocc.no/atc\\_ddd\\_index/](http://www.whocc.no/atc_ddd_index/)], frequency, drug class) of antiepileptic drugs (AEDs) from Baseline to 12 months and end of Observation Period

#### **2.2.4 Tolerability and safety variables**

The following tolerability and safety variables will be analyzed:

- Time to discontinuation of BRV due to adverse drug reactions (ADRs)
- Incidence of treatment-emergent AEs and ADRs
- Incidence of serious treatment-emergent AEs and ADRs
- Incidence of ADRs leading to discontinuation of BRV

### **2.3 Study design and conduct**

EP0077 is a postmarketing, multinational, multicenter, prospective noninterventive study (NIS) conducted at approximately 100 sites in approximately 10 European countries, with a 12-month Observation Period. Brivaracetam will be prescribed according to normal clinical practice and in accordance with the current summary of product characteristics (SmPC) in Europe for BRV. It is planned to include 530 patients in the study.

The patients will be followed as per current clinical practice. No additional clinical diagnostic or monitoring procedures will be applied. The use of an epilepsy/seizure diary, as standard clinical practice, is a requirement to enter the study. The selected questionnaires will be used if part of the standard clinical practice at the sites for the management of patients with epilepsy. The choice of medical treatment is made independently by the treating physician in the regular course of practice and is not influenced by the NIS protocol.

The clinical evaluation of patients with epilepsy will be performed by the treating physician following routine clinical practice. All visits and assessments will be scheduled and conducted per routine clinical practice. It is anticipated that each patient will have approximately 4 visits during their participation in this study. These visits will consist of:

- Visit 1, Baseline, Day 1: represents the first day of BRV treatment
- Visit 2, approximately 3 months after Baseline
- Visit 3, approximately 6 months after Baseline
- Visit 4, approximately 12 months after Baseline or end of Observation Period

### **2.4 Determination of sample size**

Initially, a sample size of 430 patients was chosen for this study in order to obtain 385 patients in the Full Analysis Set (FAS), which allows for approximately 10% of patients to not be included.

When the sample size is 385, a 2-sided 95% confidence interval (CI) for a single proportion using the large sample normal approximation will extend 0.05 from the observed proportion for an expected proportion of 0.50. As an example, given an observed retention rate of 50%, a sample size of 385 patients would give a 2-sided 95% CI of 45% to 55% based on the large sample normal approximation to the binomial distribution.

However, since the first 100 patients were all enrolled at sites in Germany in early 2016 and the enrollment in that country was closed, it was believed that ongoing enrollment in other countries would be following different best practices in BRV usage, which could lead to wide variation in this NIS. For this reason, 100 additional patients are planned to be enrolled to obtain 385 patients in the FAS at non-German sites.

It is, therefore, planned to have 530 patients, and withdrawals will not be replaced.

### **3 DATA ANALYSIS CONSIDERATIONS**

#### **3.1 General presentation of summaries and analyses**

All analysis will be performed using SAS® (Statistical Analysis System) version 9.3, or higher (SAS Institute, Cary, NC, USA).

All variables will be summarized using descriptive statistics; there will be no inferential analyses. For continuous variables, summary statistics will include number of patients with available observations (n), mean, standard deviation (SD), minimum, median and maximum. Where applicable, the 25% quartile, 75% quartile and interquartile range will also be presented. In general, the mean, SD, median, quartiles and range will be displayed to 1 more decimal place than collected in the source data. Minimum and maximum, will be displayed to the same number of decimals used for the source data.

Categorical variables will be summarized using frequencies and percentages. If there are no patients in a specific Case Report form (CRF) category or programmed set of categories, then that row will be retained and 0 presented in the table. In general, if there are patients with missing data, a missing row will be added and percentages will be based on the number of patients in the analysis set (N). Unless otherwise noted, all percentages will be displayed to 1 decimal place. No percentage will be displayed for zero counts, and no decimal will be presented when the percentage is 100%.

A complete set of data listings containing all documented data and all calculated data (eg, change from Baseline) will be generated.

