### 8.2.2.2 Derivation of seizure frequency related variables

The following variables will be defined for each visit and Month 12 /Withdrawal using the 28-day Baseline and 28-day post-Baseline seizure frequency variables described in [Section 8.2.2.1](#).

- Absolute reduction in POS frequency defined as:  
$$28\text{-day Baseline} - 28\text{-day post-Baseline seizure frequency}$$
- Percent reduction in POS frequency defined as:  
$$\frac{28\text{-day Baseline} - 28\text{-day post-Baseline seizure frequency}}{28\text{-day Baseline}} \times 100$$
- Patients with 0 POS at Baseline will be excluded from the analysis of percent reduction and response ( $\geq 50\%$ ).
- Response (Yes, No) where Yes is  $\geq 50\%$  reduction in POS frequency calculated as described above and No otherwise.
- Seizure freedom (Yes, No) will be defined using 2 methods as shown in [Table 8-1](#). The first method considers patients who withdraw prior to their 1st seizure as Not seizure free. The 2nd is a less conservative method which considers patients who withdraw prior to their 1st seizure as missing. Visit 4 (Month 12/Withdrawal) will not be summarized for seizure freedom.

Table 8–1: Derivation of seizure freedom		
Patient Classification at Visit (patients are assigned to the first category they fall into)	Seizure freedom – Discontinuations counted as not seizure free	Seizure freedom – Discontinuations counted as missing
0. Patients had a seizure before 1st BRV dose	Missing	Missing
1. Patient had a seizure on or after 1st BRV dose and on or before the visit date derived using the following conditions. First_seizure_date = Date of first seizure or if date of first seizure is missing but patient has seizures recorded at a visit, then assign first_seizure_date as the date of the visit prior to the earliest visit with seizures recorded a) Visit date present and First_seizure_date is on or after 1st BRV and on or before the Visit date b) Visit date is missing (either due to patient ongoing in study or visit missed) and First_seizure_date is on or after 1st BRV and on or before the visits target day [a])	No	No
2. Patient discontinued BRV or terminated the study prior to the visit’s target day [a]	No	Missing

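### With percentages based on the whole analysis set, the two seizure-freedom methods give the same seizure-free percentage at Months 3 and 6, and categorical outcomes with missing data are scaled down

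*SAP*

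**What the plan says.** SAP 3.1 sets the default for categorical tables: "a missing row will be added and percentages will be based on the number of patients in the analysis set (N"). For continuous variables the same section differs: "summary statistics will include number of patients with available observations (n"). SAP 8.2.2.3, 8.3.1.2, 8.3.2 and 8.3.3 ask for numbers and percentages for response, seizure freedom, QOLIE-31-P meaningful change, EpiTrack categories, CGIC and PGIC, and none of them gives a denominator of its own. SAP 5.2, by contrast, does name one for protocol deviations.

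Table 8-1 in SAP 8.2.2.2 puts each patient in the first row that applies:

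- Row 0 (seizure before the first dose) and row 3 (no seizure data at the visit, not discontinued): missing under both methods.
- Row 1 (seizure between first dose and the visit): No under both.
- Row 2, "Patient discontinued BRV or terminated the study prior to the visit" (more exactly, its target day): No under method 1; missing under method 2, whose column is labelled "Discontinuations counted as missing".
- Row 4 (none of the above, visit present): Yes under both.

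The text says that method 2 "is a less conservative method which considers patients who withdraw prior to their" first seizure as missing. A footnote restricts Month 12 to completers by setting all withdrawn patients to missing, with no distinction between methods.

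Two further statements bear on the denominator. On response: "Patients with 0 POS at Baseline will be excluded from the analysis of percent reduction and response". On the instruments, SAP 2.3: "The selected questionnaires will be used if part of the standard clinical practice at the sites for the management of patients with epilepsy".

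**The concern.** Two methods are specified so that a reader can see how far the seizure-free rate depends on the treatment of early discontinuations. That contrast works only if patients classed as missing leave the denominator. If they stay in it, relabelling them from No to missing leaves both the numerator and the denominator of the seizure-free percentage unchanged.

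The same rule affects any categorical outcome that part of the analysis set does not have. QOLIE-31-P and EpiTrack gaps are expected by design, because sites use the questionnaires only where they are routine. A percentage improved over N then combines how many patients improved with how many were assessed. The continuous summaries of the same instruments rest on available n, so means and categories for one instrument would have different bases. Seizure freedom and response are secondary variables, so this concerns results that will be read and quoted.

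**Working it through.** **1. The plan's own figure.** The documents state no expected seizure-free, responder or questionnaire rate. The only related figure is the FAS size in SAP 2.4: 1.95996² × 0.25 / 0.05² = 384.15, rounded up to 385, which reproduces. For illustration I scale it to the enlarged study: 530 × 385/430 = 474.5, so N = 475.

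**2. The identity.** Let Y be the count in row 4, W in row 2, and M in rows 0 and 3 together.

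- Denominator N: method 1 = Y/N; method 2 = Y/N, whatever W and M are.
- Non-missing denominator: method 1 = Y/(N − M); method 2 = Y/(N − M − W).

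The first line needs no assumed rate.

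**3. Size at Months 3 and 6.** Assumed: Y = 20% of N (95) and M = 5% (24), with W varied.

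| W, % of N (count) | Over N, both methods | Method 1, non-missing | Method 2, non-missing |
|---|---|---|---|
| 5% (24) | 95/475 = 20.0% | 95/451 = 21.1% | 95/427 = 22.2% |
| 10% (48) | 20.0% | 21.1% | 95/403 = 23.6% |
| 20% (95) | 20.0% | 21.1% | 95/356 = 26.7% |
| 30% (142) | 20.0% | 21.1% | 95/309 = 30.7% |

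With M = 20% (95), method 1 is 95/380 = 25.0%, and method 2 runs from 95/356 = 26.7% to 95/238 = 39.9% over the same W. With Y = 10% (48) and M = 5%, method 1 is 48/451 = 10.6%, and method 2 runs from 48/427 = 11.2% to 48/309 = 15.5%.

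The other rows of the table do differ over N. At W = 20% and M = 5%, the No row is 356/475 = 74.9% under method 1 and 261/475 = 54.9% under method 2.

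**4. Month 12.** The footnote makes withdrawn patients missing under both methods, and Protocol 8.2 withdraws anyone whose physician permanently stops brivaracetam. That leaves row 2 with nothing to separate the methods, whichever denominator they share. The N rule still changes the level. If 20% of completers were seizure free (assumed), the figure over N would be 76/475 = 16.0%, 66/475 = 13.9% or 48/475 = 10.1% with 20%, 30% or 50% withdrawn (380, 332 or 238 completers).

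**5. Other categorical outcomes.** If a share c of patients is assessed and a proportion p of those improve, the percentage over N is c × p. With p = 60% assumed, c = 30%, 50%, 70% and 90% give 18%, 30%, 42% and 54%.

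**The case against.** The default is hedged. It opens "In general, if there are patients with missing data, a missing row will be added and percentages will be based on the number of patients", and a general rule normally yields to specific text. Calling method 2 less conservative implies that missing patients drop out, and a careful programmer might act on that. The mock table shells mentioned in SAP 4.3 are not in the documents and may set denominators. This lowers the chance that the tables will be wrong. It does not settle the matter, because the effectiveness sections state no exception and the SAP says it supplies everything needed for the analysis.

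An N-based percentage with a visible missing row is also a transparent convention, and a reader can recompute. That is true, but the printed seizure-free percentages would still be equal in the comparison meant to separate them. SAP 4.6 adds analyses in completers and in patients who stopped for lack of efficacy. These are a separate look at discontinuation and do not replace the contrast between the two methods.

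Four stronger readings are tempting, and the documents do not support them:

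- *Every partly collected outcome is diluted.* Continuous summaries use available n, Kaplan-Meier analyses use censoring, and retention is a date-based yes/no with no missing category.
- *The two methods give identical tables.* Only the seizure-free percentage is identical; the No and missing rows differ.
- *Patients with no Baseline partial-onset seizures count as non-responders.* The SAP excludes them from the response analysis. Whether its N shrinks accordingly is left unsaid, which is an ambiguity and not a demonstrated error.
- *The N rule explains Month 12 as well.* There the methods coincide because of the footnote.

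**Conclusion.** The point holds for categorical effectiveness outcomes. Under the default as written, the two methods must give the same seizure-free percentage at Months 3 and 6. That follows from the definitions and rests on no assumed rate. Its size does depend on assumptions. With Y = 20% and M = 5% of N, the contrast lost is between 21.1% and a figure of 22.2% to 30.7% as discontinuation goes from 5% to 30%. The scaling of response, QOLIE-31-P, EpiTrack, CGIC and PGIC percentages equals the share assessed, for which the documents give no value.

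The primary retention analysis, its confidence interval and the sample size are untouched, and all analyses are descriptive. This is a correction the SAP should make to its secondary and other variables. It does not threaten the study's main result.

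**What to change.** - **Seizure freedom (SAP 8.2.2.3).** State that each method uses as its denominator the patients with a non-missing classification under that method: Y/(N − M) for method 1 and Y/(N − M − W) for method 2. Rows 0 and 3 then leave both, and only row 2 separates them. Keeping N for method 1 alone would not do, because rows 0 and 3 are missing under both methods. With assumed Y = 20%, M = 20% and W = 5% of N, that would show 20.0% against 26.7%, while the like-for-like figures are 25.0% and 26.7%.
- **Response, QOLIE-31-P, EpiTrack, CGIC and PGIC categories.** Use patients with a non-missing result at the visit, and completers at Visit 4 (Month 12). Confirm that patients with no Baseline partial-onset seizures are outside the response denominator. Show n/N and give missing as a count.
- **Month 12 seizure freedom.** Reconcile the Table 8-1 footnote with method 1, since changing the denominator alone cannot separate the methods there.
- **Retention.** Keep N.

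The cost is a few sentences in the SAP and footnotes in the table shells. No new data are needed.
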